## 16.3.2. Analysis of Exploratory Efficacy Variables

Exploratory efficacy variables will be summarized in a descriptive manner using ENR and mITT populations for Visits 1, 2, 3, 4 and 5.

Change in sitting DBP and SBP from Visit 1 (Week -4) will be using paired t-test. The p-value obtained from the paired t-test will be presented for the visits - Visit 2 (Week 0), Visit 3 (Week 4), Visit 4 (Week 8) and Visit 5 (Week 12). Assumption of Normality will be investigated using Wilk-Shapiro test. If the data is found to be non-Normal, then paired t-test will be replaced by Wilcoxon signed rank test. A descriptive summary using n, mean, median, SD, Q1, Q3, minimum, and maximum is also presented.

Change in mean sitting DBP and SBP for uncontrolled patients between Visit 2 (Week 0) and Visit 3 (Week 4) will be using paired t-test. The p-value obtained from the paired t-test along with n, mean, median, SD, Q1, Q3, minimum, and maximum will be presented. Assumption of Normality will be investigated using Wilk-Shapiro test. If the data is found to be non-Normal, then paired t-test will be replaced by Wilcoxon signed rank test.

The number of patients achieving standard BP goal (sitting BP < 140/90 mmHg) will besummarized for Visits 2, 3, 4 and 5, along with percentage and 95% CI for the proportion. A p-value using exact McNemar's test will be presented to compare the proportion of patients achieving the standard BP goal (sitting BP < 140/90 mmHg) between Visit 2 and Visit 3 as well as Visit 2 and Visit 4 and as well as Visit 2 and Visit 5. A p-value using McNemar's test will be presented to compare the proportion of patients achieving the BP goal (sitting BP < 140/90 mmHg) between Visit 3 and Visit 4. A two-sided p-value using McNemar's test between Visit 3 vs. Visit 5 and between Visit 4 vs. Visit 5.

Page 33 of 46

The number of patients achieving optimal BP goal (sitting BP < 130/80 mmHg in patients < 65 years old/sitting BP < 140/80 mmHg in patients  $\geq 65$  years old) will be summarized for Visits 2, 3, 4 and 5, along with percentage and 95% CI for the proportion. A p-value using exact McNemar's test will be presented to compare the proportion of patients achieving the BP goal (sitting BP < 130/80 mmHg) between Visit 2 and Visit 3 as well as Visit 2 and Visit 4 and as well as Visit 2 and Visit 5. A p-value using McNemar's test will be presented to compare the proportion of patients achieving the BP goal (sitting BP < 130/80 mmHg) between Visit 3 and Visit 4. A two-sided p-value using McNemar's test between Visit 3 vs. Visit 5 and between Visit 4 vs. Visit 5.

The number of patients achieving standard BP goal (sitting SBP/DBP < 140/90 mmHg) and the optimal BP goal (sitting BP < 130/80 mmHg in patients < 65 years old/sitting BP < 140/80 mmHg in patients  $\geq 65$  years old) will be summarized for Visits 2, 3, 4 and 5, along with percentage for each of the subgroup specified under section 7.5 of the SAP.

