- Number and proportion of patients achieving the optimal BP goal (sitting BP < 130/80 mmHg in patients < 65 years old/sitting BP < 140/80 mmHg in patients ≥ 65 years old) at Visit 5 (Week 12).
- Adherence to treatment estimated as % of doses taken/doses to be taken at Visit 2 (Week 0), Visit 3 (Week 4), Visit 4 (Week 8), and Visit 5 (Week 12).
- Safety and tolerability of the monotherapies (NEB 5 mg and RAM 5 mg) and of the extemporaneous combination (NEB/RAM 5/2.5 mg, NEB/RAM 5/5 mg, NEB/RAM 5/10 mg).

Change in sitting BP between visits will be compared using a two-sided paired t-test with 5% significance level. The p-value obtained from the paired t-test will be presented. Assumption of Normality will be investigated using Wilk-Shapiro test. If the data is found to be non-Normal, the paired t-test will be replaced by Wilcoxon signed rank test.

The continuous secondary endpoints will also be presented in a descriptive manner using n, mean, median, SD, Q1, Q3, minimum, and maximum.

The number of patients achieving the standard BP goal (sitting SBP/DBP < 140/90 mmHg) and the optimal BP goal (sitting BP < 130/80 mmHg in patients < 65 years old/sitting BP < 140/80 mmHg in patients \geq 65 years old) will be summarized for Visit 5 (Week 12). Adherence with study treatment will be assessed at Visit 2 for monotherapy and Visit 3, Visit 4, and Visit 5 for the combination therapy. The amount of study treatment taken by the patient will be derived by counting the number of tablets in the blister returned and will be recorded in the source document and in the eCRF.

Adherence to treatment will be estimated by using the below formula: *(number of doses taken during the study)/(number of doses to be taken during the study)*×100

MENARING	Global Medical Department		
		Protocol Template	
Identification Number	Version Number	State	Effective date
FORM-000050125	3.0, CURRENT	Effective	13 May, 2022

A patient who has taken at least 80% and no more than 120% of the required study medication intake since the last visit will be considered as compliant.

Exploratory (efficacy) analysis

Exploratory efficacy variables will be summarized in a descriptive manner using enrolled population for Visits 1, 2, 3, 4 and 5.

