#### 5. ANALYSIS SETS

All population sets for analysis will be discussed with sponsor for statistical analysis during data review meeting and Agreement and authorization of subjects included/excluded from each analysis set will be conducted prior to the database lock of the study.

After an Audit conducted by the Sponsor, the Site 114 has been closed for GCP non-compliance due to data quality issues. These data will be cleaned regularly, as for all other sites, but these will not be included in the Modified Intent-to-Treat (mITT) and Per Protocol (PP) analysis sets. The Sponsor decision process and relevant assessment for the Site closure will be summarized in the Clinical Study Report. To verify the impact of this exclusion on the study results, the primary efficacy analysis will be conducted both with data from site 114 and without data from site 114.

Page 18 of 46

Data from this site will not be excluded from the safety analysis and sensitivity mITT analysis on primary efficacy endpoint (see chapter 16.4).

After two For Cause Audits (one conducted by CRO Indipendent QA Department and the other conducted by the Sponsor), patients from Site 507 for whom "Primary efficacy source data are unavailable or unreliable" will not be included in the Modified Intent-to-Treat (mITT) and so in the Per Protocol (PP) analysis sets. The Sponsor decision process and relevant assessment for the exclusion of these patients will be summarized in the Clinical Study Report. To verify the impact of this exclusion on the study results, the primary efficacy analysis will be conducted both with data from these patients and without data from these patients.

Data from these patients will not be excluded from the safety analysis and sensitivity mITT analysis on primary efficacy endpoint (see chapter 16.4).

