## 5.1. All Subjects Enrolled Set [ENR]

The Enrolled (ENR) population will contain Patients who are enrolled into the study (i.e., signed ICF and met the eligibility criteria) and may or may not receive the study treatment (monotherapy and/or combination therapy).

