## 7.5. Examination of Subgroups

Subgroup analyses will be conducted as stated in the exploratory analysis sections. It should be noted that the study was not designed to detect treatment differences with high statistical power within subgroups.

The following subgroups will be assessed and described within the exploratory analysis sections on ENR and mITT populations respectively.

- Hypertension grade at screening
- CHD
- Presence of diabetes (patients with or without diabetes) at screening
- Presence of hypercholesterolemia (patients with or without hypercholesterolemia) at screening

Hypertension grade at screening is derived as follows;

```
140 <= SBP < 160 or 90 <= DBP <100
160 <= SBP < 180 or 100 <= DBP <110
```

Patients with hypercholesterolemia at screening can be identified based on the clinical significance of the total cholesterol value collected in the blood chemistry laboratory data. If the total cholesterol at screening has clinical significance as per the investigator's input, then the patient will be considered for hypercholesterolemia and the details will be entered in the medical history data.

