## 16.4 Sensitivity Analysis Including Data from Site(s) with Data Quality Issues

For Site 114 excluded for data quality issues, sensitivity analysis will be performed including data on the primary efficacy endpoint.

For the patients from Site 507 excluded for primary efficacy source data unavailable or unreliable data, sensitivity analysis will be performed including data on the primary efficacy endpoint.

Variable	Analysis set	Analysis type
Change in mean sitting SBP between Visit 2 (Week 0) and Visit 5 (Week 12)	mITT including all patients (all patients from Site 114 and Site 507)	Paired t-test

In the case of a significant difference between the results of the two primary efficacy analyzes (mITT vs. mITT including all patients), the efficacy outcome (primary, secondary and exploratory) variables will be analyzed using both the mITT as well as the "mITT including all patients" population. All results of the "mITT including all patients" analysis will be reported in the CSR.

Data from Site 114 and from those patients from Site 507 for whom primary efficacy data are unavailable or unreliable will not be excluded from the safety analysis.

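### Exploratory efficacy outputs on the Enrolled set still take in the blood pressure data of Site 114 and the flagged Site 507 patients, which the SAP removes from its other planned efficacy sets

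*SAP*

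**What the plan says.** **The exclusion.** SAP 5 records that "the Site 114 has been closed for GCP non-compliance due to data quality issues" and that its data will "not be included in the Modified Intent-to-Treat (mITT) and Per Protocol (PP) analysis sets". For Site 507 the exclusion covers individual patients only: those whose source data for the primary endpoint could not be found or relied on. SAP 5.2 writes both exclusions into the mITT definition, and PP is a subset of mITT. For both groups, SAP 5 names two uses in which the data stay: the safety analysis and a sensitivity mITT analysis of the primary endpoint.

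**The Enrolled set.** SAP 5.1 defines it as patients who "signed ICF and met the eligibility criteria) and may or may not receive the study treatment". No site or data-quality exclusion is attached.

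**The exploratory outputs.** SAP 16.3.2: "Exploratory efficacy variables will be summarized in a descriptive manner using ENR and mITT populations for Visits 1, 2, 3, 4 and 5". SAP 7.5: "The following subgroups will be assessed and described within the exploratory analysis sections on ENR and mITT populations respectively". The protocol named the Enrolled set alone (section 12.5): "Exploratory efficacy variables will be summarized in a descriptive manner using enrolled population for Visits 1, 2, 3, 4 and 5". The SAP added mITT.

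**The conditional route.** SAP 16.4 extends the analysis of all efficacy variables, exploratory ones included, to an mITT set with all patients restored. It does so only "In the case of a significant difference between the results of the two primary efficacy analyzes".

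**The concern.** Blood pressure readings that were judged unfit for the main efficacy sets come back in the Enrolled-set efficacy tables, and no text says that this is intended. Those tables are more than descriptive. SAP 16.3.2 plans paired t-tests (or Wilcoxon signed rank tests) on changes from Visit 1, McNemar tests on goal attainment, and 95% confidence intervals for the proportions. It also plans goal rates by hypertension grade, CHD, diabetes and hypercholesterolemia.

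At stake are exploratory estimates and p-values in the population that the protocol named for them. No rule tells the programmer to drop these patients or to flag the tables that contain them. If the question is first raised after results are known, the choice of version will look driven by the results.

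**Working it through.** **Step 1. Where the excluded data go, output by output.**

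| Output | Set | Excluded data used? |
|---|---|---|
| Primary (SAP 16.1.3) and MMRM (16.1.4) | mITT | No |
| PP sensitivity analysis (16.1.5) | PP | No |
| Secondary (16.2) | mITT, PP | No |
| Site sensitivity analysis, primary endpoint (16.4) | mITT with all patients | Yes, stated in 3.3, 5 and 16.4 |
| Safety (18) | Safety set | Yes, stated in 3.3, 5 and 16.4 |
| Exploratory (16.3.2, 7.5) | mITT | No |
| Exploratory (16.4) | mITT with all patients | Only if the two primary results differ |
| Exploratory (16.3.2, 7.5) | Enrolled | Yes, unconditionally, and stated nowhere |

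Only the last row lacks a stated decision.

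**Step 2. Can the pre-lock agreement on set membership (SAP 5) settle it?** Not under the written definition. SAP 5.1 admits every eligible patient with a signed consent, so it gives no ground for removing these patients. The set also has to keep them, because disposition (9.1), deviations (9.2) and demographics (10) are reported on it. The rule has to sit at the level of the output, and none is written there.

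**Step 3. Can the mITT version stand in?** Only in part. mITT requires a dose of combination therapy and blood pressure at Weeks 0 and 12 (5.2). Patients controlled at Visit 2 are withdrawn (3.1), and the control thresholds are the same as the optimal-goal thresholds. If the rules are followed, the Visit 2 optimal-goal rate in mITT is therefore about zero by design. Visit 1 to Visit 2 changes in mITT likewise leave out the patients who became controlled during run-in. For these outputs the Enrolled set is the informative one.

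**Step 4. Size.** The plan gives no figure for these outputs and no count of affected patients, so only a range under assumptions is possible.

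- Inputs: 270 screened (Protocol 12.2) and about 26 sites (Protocol 5, SAP 3.1). The plan's 270 is consistent with its own basis: 215/(1 − 0.20) = 268.75, or 269, against 270 stated.
- Average per site: 270/26 = 10.4. Two sites: 20.8, about 21.
- Share f: 1/26 = 3.8%; 2/26 = 7.7%.
- Shift in an Enrolled-set mean change = f × d, where d is the difference in mean change between affected patients and the rest. The documents give no value for d, so it is assumed.

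| Share f | d = 5 mmHg | d = 10 mmHg |
|---|---|---|
| 3.8% | 0.19 | 0.38 |
| 7.7% | 0.38 | 0.77 |

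The Enrolled set omits screen failures, so 270 is only a proxy for its size. The share f is unaffected if screen failure is similar across sites. The same formula applies within a subgroup, where f could be larger, but the documents offer nothing to size it.

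**The case against.** The best opposing case is that little depends on this. Every analysis that carries the trial's conclusion already omits these data, and the exploratory outputs are also run on mITT. The protocol prespecified the Enrolled set. Leaving it whole as an all-patients view beside mITT, with a footnote, is a respectable choice, whereas trimming it after audits in an open-label trial departs further from the protocol. The table shells approved with the SAP (section 4) are not among the documents reviewed and may already carry a footnote. All of this stands as an argument for moderate severity and for accepting a clearly stated alternative. It does not supply the missing statement.

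A reader might also infer more than the documents support:

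- **That 16.4 and 16.3.2 contradict each other.** Section 16.4 governs when a separate all-patients mITT set is run and does not mention the Enrolled set. Both instructions can be carried out as written. The condition in 16.4 is bypassed, not broken.
- **That the reason for a difference between Enrolled and mITT tables would be hidden.** SAP 3.3 and 5 send the exclusion decisions to the Clinical Study Report, and 9.1 tabulates the reasons for exclusion from each set. The two tables would differ in any case, because the Enrolled set keeps patients withdrawn at Visit 2 and those without Week 12 data. What is missing is a label on the tables.
- **That all of Site 507 is excluded, or that Site 114's data were called unreliable.** Only flagged Site 507 patients are excluded, and where their data are unavailable there may be little to include. For Site 114 the stated ground is GCP non-compliance arising from data quality issues.

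**Conclusion.** The inconsistency is real and of moderate weight. Followed as written, the SAP puts blood pressure data that it removed from mITT and PP into the exploratory efficacy outputs on the Enrolled set, and its list of permitted uses does not cover this. The primary, PP and secondary analyses are not affected.

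The likely shift in an Enrolled-set mean change is about 0.4 to 0.8 mmHg. This rests on two assumptions: that the affected patients number one to two average sites, and that their mean change differs from the rest by 10 mmHg. At 5 mmHg the shift is about 0.2 to 0.4 mmHg. The 2.4 mmHg design difference in Protocol 12.2 belongs to the primary endpoint and should not be read as a threshold here. A reader might reach for a larger shift by assuming many more affected patients, but one site and part of another give no basis for that.

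**What to change.** Before database lock:

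1. In SAP 16.3.2 and 7.5, state that Enrolled-set efficacy outputs are run without Site 114 and the flagged Site 507 patients.
2. Leave the definition in 5.1 unchanged, so that the set stays whole for disposition, demographics and deviations. Keep these patients in the safety set.
3. Label any full Enrolled-set efficacy version as a sensitivity output.
4. Record the change in 3.3, since the protocol names the Enrolled set for these outputs.

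If the sponsor wants these data in the Enrolled-set efficacy tables, the minimum is to say so in 3.3, 5 and 16.4 and to footnote each table.

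The cost is a short SAP amendment and one more population flag in programming, with matching shell changes because SAP 4 ties the shells to the SAP. The downside is a slightly smaller n in the exploratory tables.

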 To assess the antihypertensive efficacy in terms of sitting DBP and SBP between Visit 1 (Week -4) and Visit 2 (Week 0), Visit 3 (Week 4), Visit 4 (Week 8), and Visit 5 (Week 12) in the overall population. 	• Change in mean sitting DBP and SBP between Visit 1 (Week -4) and Visit 2 (Week 0), Visit 3 (Week 4), Visit 4 (Week 8), and Visit 5 (Week 12) in the overall population.	To gain specific knowledge on the antihypertensive effect of the extemporaneous combination in patients uncontrolled after 30 days of combined therapy.
 To evaluate sitting DBP and SBP between Visit 1 (Week -4) and Visit 2 (Week 0), Visit 3 (Week 4), Visit 4 (Week 8) and Visit 5 (Week 12) in patients who were on NEB 5 mg and RAM 5 mg at Visit 1 and continued to be on the same therapies or who switched to NEB 5 mg or RAM 5 mg from any other beta blocker (BB) or angiotensin-converting enzyme inhibitors (ACE- is) at Visit 1. 	 Change in mean sitting DBP and SBP between Visit 1 (Week -4) and Visit 2 (Week 0), Visit 3 (Week 4), Visit 4 (Week 8), and Visit 5 (Week 12) in the following subgroups: in the group of patients who were on NEB 5 mg and RAM 5 mg at Visit 1 and continued to be on the same therapies. in the group of patients who switched to NEB 5 mg or RAM 5 mg from any other BB or ACE- i at Visit 1. 	Evaluation of the antihypertensive efficacy of combination therapy in the subgroup of patients who were on nebivolol or on ramipril at the inclusion in the study or who switched from a different BB or ACE-i will provide useful information on the impact (if any) that previous monotherapies have on the antihypertensive effect of the extemporaneous combination.
• To evaluate sitting DBP and SBP at Visit 3 (Week 4), Visit 4 (Week 8), and Visit 5 (Week 12) in patients with uncontrolled hypertension.	• Mean sitting DBP and SBP for uncontrolled patients at Visit 3 (Week 4), Visit 4 (Week 8), and Visit 5 (Week 12).	To gain specific knowledge on the antihypertensive effect of the extemporaneous combination in patients uncontrolled after 30 days of combined therapy.

MENARINI	Global Medical Department		
	Protocol Template		
Identification Number	Version Number State Effective date		
FORM-000050125	3.0, CURRENT	Effective	13 May, 2022

OBJECTIVES	ENDPOINTS	JUSTIFICATION FOR ENDPOINTS

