#### 6.5. Statistical Tests

The default significant level will be (5%); confidence intervals will be 95% and all tests will be two-sided, unless otherwise specified in the description of the analyses.

Page 20 of 46

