## 16.3. Exploratory Efficacy

## 16.3.1. Exploratory Efficacy Variables & Derivations

Change in mean sitting DBP and SBP between Visit 1 (Week -4) and Visit 2 (Week 0), Visit 3 (Week 4), Visit 4 (Week 8) and Visit 5 (Week 12):

- In the group of patients who were on NEB 5 mg and RAM 5 mg at Visit 1 (Week -4) and continued to be on the same therapies.
- In the group of patients who switched to NEB 5 mg or RAM 5 mg from any other BBs or ACEs at Visit 1 (Week -4).

To assess change in mean sitting DBP and SBP, for uncontrolled patients at Visit 3 (Week 4), between Visit 2 (Week 0) and Visit 3 (Week 4).

To assess change in mean sitting DBP and SBP, for uncontrolled patients at Visit 4 (Week 8), between Visit 2 (Week 0) and Visit 4 (Week 8) and between Visit 3 (Week 4) and Visit 4 (Week 8).

Number and proportion of patients achieving the standard BP goal (sitting SBP/DBP < 140/90 mmHg) at Visit 2 (Week 0), Visit 3 (Week 4), Visit 4 (Week 8) and Visit 5 (Week 12): In the group of patients who were on NEB 5 mg and RAM 5 mg at Visit 1 (Week -4) and continued to be on the same therapies.

In the group of patients who switched to NEB 5 mg or RAM 5 mg from any other BBs or ACEs at Visit 1 (Week 4).

Number and proportion of patients the optimal BP goal (sitting BP < 130/80 mmHg in patients <65 years old/sitting BP < 140/80 mmHg in patients  $\geq$  65 years old) at Visit 2 (Week 0), Visit 3 (Week 4), Visit 4 (Week 8) and Visit 5 (Week 12):

In the group of patients who were on NEB 5 mg and RAM 5 mg at Visit 1 (Week -4) and continued to be on the same therapies.

In the group of patients who switched to NEB 5 mg or RAM 5 mg from any other BBs or ACEs at Visit 1 (Week 4).

Page 32 of 46

Number and proportion of patients divided into subgroups according to the hypertension grade, CHD, the presence of diabetes and/or of hypercholesterolemia achieving the standard BP goal (sitting SBP/DBP < 140/90 mmHg) at Visit 2 (Week 0), Visit 3 (Week 4), Visit 4 (Week 8) and Visit 5 (Week 12).

In the group of patients who were on NEB 5 mg and RAM 5 mg at Visit 1 (Week -4) and continued to be on the same therapies.

In the group of patients, who switched to NEB 5 mg or RAM 5 mg from any other BBs or ACEs at Visit 1.

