## **Reference Code**

Paired t-test

```
ods trace on;

proc ttest data=input_data h0=0;

paired VISITX*VISITY;

ods output TTests=test;

run;

ods trace off;
```

Normality assumption check

```
ods trace on;

proc univariate data=indata normal plot;

var change from baseline;

histogram /normal kernel(color=red);

ods output TestsForNormality=norm(where=(test="Shapiro-Wilk"));

run;

ods trace off;
```

Wilcoxon Signed Rank Test

Page 43 of 46

Statistical Analysis Plan v 3.0

run;

```
ods trace on;
proc univariate data=indata mu0=0 loccount;
  var change from baseline;
  ODS Output TestsForLocation=test LocationCounts=LOCC one;
       Exact McNemars Test
ods trace on;
ods output McNemarsTest=McNemarsTest;
proc freq data=indata order=data;
  tables VISITX*VISITY/agree alpha=0.05;
  exact mcnem;
  weight ZZZ/zeros;
run;
       Independent sample t-test
ods trace on:
proc ttest data=indata h0=0;
class xxx;
var change from baseline;
run;
ods trace off:

    Wicoxon Rank Sum Test

ods trace on;
proc npar1way data=indata wilcoxon;
  by by variables;
  class xxx;
  var change from baseline;
  ods output WilcoxonTest=wt;
run:
       Repeated measures Mixed Model
proc mixed data=indata;
class visit sex;
model change from baseline = Visit Age Gender BMI baseline SBP Age*Gender
Age*BMI Age*baseline SBP Gender*BMI Gender*baseline SBP BMI*baseline SBP
Age*Gender*BMI Age*Gender*baseline SBP Age*BMI*baseline SBP Gender*BMI*baseline SBP
Age*Gender*BMI*baseline SBP;
repeated visit;
```

**■IQVIA**™

Imputed dates will NOT be presented in the listings.

Algorithm for Treatment Emergence of Adverse Events:

START DATE	STOP DATE	ACTION
Known	Known/Partial/	If start date < study med start date, then not
	Missing	TEAE
		If start date >= study med start date, then TEAE
Partial, but known	Known/Partial/	Not TEAE
components show that it	Missing	
cannot be on or after		
study med start date		
Partial, could be on or	Known	If stop date < study med start date, then not
after study med start		TEAE
date		If stop date >= study med start date, then TEAE
OR Missing		
	Partial	Impute stop date as latest possible date (i.e. last
		day of month if day unknown or 31st December if
		day and month are unknown), then:
		If stop date < study med start date, then not
		TEAE
		If stop date >= study med start date, then TEAE
	Missing	Assumed TEAE

Page 45 of 46

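### The plan gives no between-group estimate for the question of whether previous monotherapy affects the response to the combination; the planned paired tests address only whether blood pressure changed

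*SAP*

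**What the plan says.** The exploratory objectives in Protocol section 4 include blood pressure change from Visit 1 in two subgroups: patients already on nebivolol 5 mg or ramipril 5 mg who stayed on it, and patients moved to one of these from another beta blocker or ACE inhibitor. The justification column says that this will give "useful information on the impact (if any) that previous monotherapies have on the antihypertensive effect of the extemporaneous combination".

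SAP 16.3.1 lists change from Visit 1 to Visits 2, 3, 4 and 5 under two headings. One covers the patients who stayed on their existing drug; the other is "In the group of patients who switched to NEB 5 mg or RAM 5 mg from any other BBs or ACEs at Visit 1".

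SAP 16.3.2 first says that exploratory variables will be summarised descriptively, on the ENR and mITT sets. It then states: "Change in sitting DBP and SBP from Visit 1 (Week -4) will be using paired t-test", with a p-value at each of Visits 2 to 5, the Wilcoxon signed rank test as fallback, and n, mean, median, SD, quartiles and range. The reference code for the paired test is "proc ttest data=input_data h0=0", so the null is zero mean change. SAP 6.5 sets the level at 5% and says that "all tests will be two-sided, unless otherwise specified in the description of the analyses".

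**The concern.** To learn whether previous monotherapy has an impact on the combination's effect, one compares the mean change in switched patients with the mean change in continued patients. The matching null is equal mean change. A paired test within one group has a different null, no change in that group, and rejecting or not rejecting it says nothing direct about the other group.

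Two misreadings become possible. If blood pressure falls clearly in both groups, both p-values are small and a real difference between groups goes unseen. If one group is small, it may miss significance although both respond alike, and previous therapy then appears to matter when it does not.

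The starting visit is a further difficulty. Change from Visit 1 includes the four-week run-in and, for switched patients, the change of drug. The justification asks about the effect of the combination, which begins at Visit 2.

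**Working it through.** **1. Is the comparison planned elsewhere?**
- SAP 16.1.4, MMRM: visit, age, gender, BMI, baseline SBP and interactions among the covariates. There is no term for previous therapy. The models in 16.2.1.1 to 16.2.1.3 follow the same pattern.
- SAP 16.2.1.4 and 16.2.1.5: independent-samples t-tests, but only between dose groups.
- SAP 16.2.1.6, 16.2.1.7 and 16.3.2: McNemar tests, which compare visits and not groups.
- Protocol 12.5: paired tests between visits only.

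No contrast, interaction or interval for switched versus continued patients was found. If 16.3.2 is applied by group, it yields 2 groups × 2 pressures × 4 visits = 16 p-values per analysis set, none of which tests the difference.

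**2. Inputs.** Protocol 12.2 gives 215 completers, SD 12.0 mmHg, null mean 3.0 and alternative mean 5.4 mmHg. Its sample size reproduces: (12 × (1.645 + 1.282) / 2.4)² = 214.1, so 215. Inflation gives 215 / 0.80 = 269, against 270 stated. That calculation is not in dispute; it supplies the SD.

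Two inputs are assumptions. The documents give no group sizes, so splits from 108/107 to 194/21 are used. The SD of 12 belongs to the primary endpoint and is applied here to both groups.

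**3. Formulas.** All tests are two-sided at 5%.
- Within-group power for true change d in n patients: noncentral t, n − 1 df, noncentrality d√n / 12.
- Exactly one of two independent groups significant: p₁(1 − p₂) + p₂(1 − p₁), where p₁ and p₂ are the two powers.
- Direct test of a difference D: noncentral t, 213 df, noncentrality D / SE, with SE = 12 × √(1/n₁ + 1/n₂). The 95% CI half-width is 1.971 × SE.

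Example: 172/43 with a true fall of 3 mmHg in both groups. The powers are 0.903 and 0.360, so 0.903 × 0.640 + 0.360 × 0.097 = 0.61.

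**4. Results.** Columns 2 to 4 give the chance that exactly one group is significant when the true falls are equal.

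| Split | 3 mmHg in both | 5.4 mmHg in both | 12 mmHg in both | Direct test: power for a 6 mmHg difference | CI half-width (mmHg) |
|---|---|---|---|---|---|
| 108/107 | 40% | 1% | about 0% | 95% | 3.2 |
| 150/65 | 49% | 5% | about 0% | 92% | 3.5 |
| 172/43 | 61% | 18% | about 0% | 83% | 4.0 |
| 194/21 | 77% | 50% | 1% | 58% | 5.4 |

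A direct test has a 5% false-positive rate in every row with equal falls.

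**5. One data set.** Suppose that both groups show an observed mean fall of 3.0 mmHg. With n = 43, the standard error is 12/√43 = 1.83, t = 1.64 and p = 0.109. With n = 172, it is 0.915, t = 3.28 and p = 0.001. The observed difference is zero.

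**6. A true 6 mmHg difference (5.4 versus 11.4).** If the smaller group has the larger fall, the p-values disagree in at most 1.5% of trials in any split. If the larger group has the larger fall, they disagree in about 5% (150/65), 18% (172/43) and 50% (194/21). The last figure equals the one for no difference at all, with 5.4 mmHg in both groups, so the pattern of significance does not separate the two cases.

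**The case against.** The strongest reply is that the plan commits to little here. The objective is only to evaluate blood pressure in these patients. The wording on impact stands in a justification column and promises no more than useful information. SAP 16.3.2 calls the analysis descriptive, and SAP 7.5 warns that the study was not designed for high power within subgroups. If means and SDs are shown by group, a reader can work out a crude difference.

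Much of this stands. A reader might infer that the trial will judge the impact of previous therapy by comparing two p-values. No passage says so. Section 16.3.2 does not even repeat that the test is run by group, and change from Visit 1 is also an exploratory endpoint in the overall population, for which a test against zero is legitimate. The link to the two groups comes from reading 16.3.2 with 16.3.1.

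A reader might also infer that within-group p-values always cost a large amount of power. They do not. At 194/21 with the larger fall in the larger group, they disagree in 50% of trials, against 58% power for the direct test. The loss depends on which group responds more.

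What remains is the gap itself. Low power does not repair a mismatched null. A difference worked out by a reader would be unadjusted and unplanned.

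**Conclusion.** The point holds as an omission: the plan names a between-group question and provides no between-group estimate for it. The p-values that would be printed cannot fill the gap. When both groups truly respond alike, their agreement or disagreement is driven by group size and by how large the common fall is.

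The size of the problem depends on assumptions. It is marked if the common fall is about 3 mmHg or the split is very uneven, and negligible if both groups fall by about 12 mmHg. Group sizes are unknown, and the SD of 12 mmHg is borrowed from the primary endpoint.

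Severity is low. The objective is exploratory, and neither the primary analysis nor its conclusion depends on it. It is worth correcting because the correction is cheap.

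**What to change.** In SAP 16.3.2, before database lock, add the switched-minus-continued difference in mean change of sitting SBP and of sitting DBP from Visit 2 to Visit 5, and likewise to Visits 3 and 4, each with a 95% CI. Estimate it from a linear model with group, run-in drug (nebivolol or ramipril) and Visit 2 blood pressure as terms. Use the mITT set, which is defined by having the Week 0 and Week 12 primary data.

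Starting at Visit 2 separates the combination's effect from the run-in and the drug switch. Keep the within-group changes from Visit 1 as description. State that any remark on previous therapy rests on the estimated difference and its CI, and that it is an exploratory association, since the groups are not randomised.

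The cost is one extra model with its table rows, from data already collected, plus SAP wording. The drawback is modest precision. The unadjusted half-width is about 3.2 to 5.4 mmHg across the assumed splits, so the result should be presented as an estimate and not as a verdict of significance.
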